2 PROTOCOL ACTIVITIES BY VISIT

Study visits may be impacted due to cases of state of emergency or pandemic situations. This may include changes such as phone or virtual visits, visits at alternative locations, or changes in the visit frequency and timing of study procedures, among others. Additional details are provided in the subsequent sections. Every effort should be made to ensure the safety of subjects and site staff, while maintaining the integrity of the study. If visits cannot be conducted on-site due to travel restrictions or other state of emergency or pandemic-related reasons, follow the updates below on how to proceed. Supplemental study case report forms should be completed in the event of missed/virtual visits, or study drug interruptions or discontinuations related to coronavirus disease 2019 (COVID-19).

2.1 Individual Treatment Period Visit Activities

This section presents a list of activities performed during each visit, organized by visit. The dot pattern on the upper right indicates the place of the visit in the overall Treatment Period Activity Schedule.

Subjects will be allowed a visit window of \pm 3 days for all study visits (with the exception of the Baseline Visit, as the screening window is a maximum of 35 days) up to the Week 16 visit. Visits after the Week 16 visit will have a visit window of \pm 7 days.

Activities are grouped by category (Interview, Exam, etc.). Further information about each activity is provided in Section 3.

State of Emergency or Pandemic-Related Acceptable Protocol Modifications

During a state of emergency or pandemic situation, if it is not possible for all study procedures to be performed as specified due to travel restrictions or other reasons, the following modifications are allowed:

- If permitted by local regulations, the Institutional Review Board (IRB)/ Independent Ethics Committee (IEC), and the subject, some study visits and/or activities may be performed by phone/virtually. These are indicated by a hashtag (#) in the appropriate visit table(s) below.
- Some study visits and/or activities may be performed by a local clinic/hospital/laboratory. These are indicated by a plus sign (+) in the appropriate visit table(s) below. All procedures performed at local facilities must be performed by appropriately qualified personnel.
- Study visits and/or activities should be performed as scheduled whenever possible. If it is not possible to do so due to the pandemic, the following modifications should be followed:
 - The Screening, Baseline, and Week 12 visits should be performed on-site only.
 - If an activity is missed during a virtual visit, perform the activity at the earliest feasible
 opportunity. Laboratory draws for safety assessments should be obtained as soon as
 feasible and preferably within the protocol-defined visit window for the scheduled visit.
 Blood samples for PK assay that cannot be performed on-site for a specific visit will be
 considered missed.

No use or disclosure outside AbbVie is permitted without prior written authorization from AbbVie.

SCREENING:

□ INTERVIEW	 Subject information and informed consent^a Eligibility criteria Medical/surgical history Hidradenitis suppurativa (HS) history Alcohol and nicotine use 	 Prior/concomitant therapy Adverse event (AE) assessment^b Tuberculosis (TB) risk assessment questionnaire^c Review and document continued compliance with pregnancy avoidance recommendations in the source records with females of childbearing potential
■ PRO	 Dispense handheld electronic patient reported outcome (ePRO) device and the paper diary (for Analgesic Use for HS-related pain) for initiation of daily data collection 	 Patient's Global Assessment (PGA) Skin Pain^d Analgesic Use^d Hidradenitis Suppurativa Symptom Assessment (HSSA)^d
* EXAM	 Electrocardiogram (ECG)^e Height, weight Vital signs 	 Physical examination Chest X-ray (CXR)^f
LOCAL LAB	 Purified protein derivative (PPD) skin test^g 	Beta-D-glucan (Japan only)
▲ CENTRAL LAB	 Hematology Blood chemistry Urinalysis QuantiFERON-TB Gold Plus test^g Hepatitis B virus (HBV)/hepatitis C virus (HCV) screening 	 Anti-human immunodeficiency (HIV) testing^h Follicle stimulating hormone (FSH)ⁱ Serum pregnancy test^j

•0000000000

NOTES:

All screening procedures must be performed on-site.

- a. Obtain informed consent prior to performing any study-related procedures.
- b. Collect serious adverse events (SAEs) and protocol-related nonserious AEs that occur after a subject signs the informed consent, prior to the first dose of study dug (refer to Section 4.1 for additional details).
- c. Complete entire form (Part I and Part II).
- d. PGA Skin Pain and Analgesic use (for HS-related pain) will be collected daily from at least 7 consecutive days prior to Baseline. HSSA will be collected for 7 consecutive days prior to Baseline.
- e. Screening ECG not required if subject had normal ECG within 90 days of Screening (refer to Section 3.12 for additional details).
- f. Screening CXR not required if subject had normal CXR (posterior-anterior and lateral views) within 90 days of Screening (refer to Section 3.13 for additional details).
- g. The QuantiFERON-TB Gold Plus test (or equivalent) should be performed on all subjects. The PPD skin test should be utilized when the QuantiFERON-TB Gold Plus test (or equivalent) is not possible or if both tests are required per local guidelines.

p. 6 of 47

- h. Anti-HIV Ab performed at Screening, unless prohibited by local regulations (refer to Section 3.19 for additional details).
- i. FSH tested at Screening if female subject is ≤ 55 years of age AND has had no menses ≥ 12 months AND has no history of permanent surgical sterilization (refer to Section 3.19 for additional details).
- j. For all females of childbearing potential (refer to Section 3.19 for additional details).

BASELINE VISIT^a (DAY 1):

\circ	0	0	O	\circ	O	O	\circ	O	\circ

□ INTERVIEW	 Eligibility criteria Medical/surgical history HS history Prior/concomitant therapy 	 AE assessment Review and document continued compliance with pregnancy avoidance recommendations in the source records with females of childbearing potential
■ PRO	 PGA Skin Pain^b Analgesic Use^c HSSA^d 	 Hidradenitis Suppurativa Impact Assessment (HSIA) Dermatology Life Quality Index (DLQI)
* EXAM	WeightVital signsPhysical examination	 Inflammatory lesion count (abscess, inflammatory nodule, and draining fistula/tunnel count) Hurley stage
LOCAL LAB	 Urine pregnancy test^e 	
▲ CENTRAL LAB	 Hematology Blood chemistry Urinalysis High-sensitivity C-reactive protein (hsCRP) Total cholesterol, high-density lipoprotein cholesterol (HDL-C), low-density lipoprotein cholesterol (LDL-C), and triglycerides (fasting) 	 Blood samples for pharmacokinetic (PK) assay Optional blood samples for biomarkers:^f whole blood ribonucleic acid (RNA), whole blood deoxyribonucleic acid (DNA), plasma/serum proteomic, immunoglobulin G (IgG) and B cell subsets, and peripheral blood mononuclear cells (PBMC)
R TREATMENT	RandomizationDispense study drug and dosing diary	

NOTES:

All Day 1 procedures must be performed on-site.

- a. Baseline Visit procedures will serve as reference for all subsequent visits with the exception of ECG (obtained at Screening only and used as the baseline reference).
- b. PGA Skin Pain is collected daily from at least 7 consecutive days prior to Baseline through Week 16 and then daily for 7 consecutive days prior to the Week 24, Week 32, Week 40, and Week 48/PD visits.

- Analgesic use for HS-related pain is collected daily from at least 7 consecutive days c. prior to Baseline through Week 16.
- HSSA is collected for 7 consecutive days prior to Baseline, Week 2, Week 4, Week 8, d. Week 12, Week 16, Week 24, and Week 48/PD visits.
- For all females of childbearing potential, collect urine for pregnancy test (refer to e. Section 3.19 for additional details).
- f. Samples should be collected pre-dose.

WFFK 2a:

□ INTERVIEW	# AE assessment # Concomitant therapy	# Review and document continued compliance with pregnancy avoidance recommendations in the source records with females of childbearing potential
■ PRO	 PGA Skin Pain^b Analgesic Use^c 	HSSA ^d
* EXAM	WeightVital signs	 Inflammatory lesion count (abscess, inflammatory nodule, and draining fistula/tunnel count)
5 LOCAL LAB	#,+ Urine pregnancy test ^{e,f}	
CENTRAL LAB	+ Hematology + Blood chemistry	hsCRP Blood samples for PK assay ^g

	CENTR	RAL LA	٨B
--	-------	--------	----

- R TREATMENT
- Dispense study drug and dosing diary

NOTES:

- Subjects will be brought back to their original visit schedule (calculated from a. Baseline) if they are out of the visit window, for all visits indicated.
- PGA Skin Pain is collected daily from at least 7 consecutive days prior to Baseline b. through Week 16 and then daily for 7 consecutive days prior to the Week 24, Week 32, Week 40, and Week 48/PD visits.
- Analgesic use for HS-related pain is collected daily from at least 7 consecutive days c. prior to Baseline through Week 16.
- d. HSSA is collected for 7 consecutive days prior to Baseline, Week 2, Week 4, Week 8, Week 12, Week 16, Week 24, and Week 48/PD visits.
- For all females of childbearing potential, collect urine for pregnancy test (refer to e. Section 3.19 for additional details).
- If urine pregnancy tests cannot be performed on-site or at home due to COVID-19, f. urine pregnancy tests may be performed by a local lab.
- Blood samples for PK assay that cannot be performed on-site for a specific visit due g. to COVID-19 will be considered missed.

WEEK 4a:

INTERVIEW	# AE assessment # Concomitant therapy	# Review and document continued compliance with pregnancy avoidance recommendations in the source records with females of childbearing potential
■ PRO	 PGA Skin Pain^b Analgesic Use^c 	 HSSA^d HSIA
* EXAM	WeightVital signs	 Inflammatory lesion count (abscess, inflammatory nodule, and draining fistula/tunnel count)
LOCAL LAB	#,+ Urine pregnancy test ^{e,f}	
▲ CENTRAL LAB	 Hematology Blood chemistry Urinalysis hsCRP 	 Optional blood samples for biomarkers:^g whole blood RNA, plasma/serum proteomic, IgG and B cell subsets
R TREATMENT	Dispense study drug and dosing	

NOTES:

- a. Subjects will be brought back to their original visit schedule (calculated from Baseline) if they are out of the visit window, for all visits indicated.
- b. PGA Skin Pain is collected daily from at least 7 consecutive days prior to Baseline through Week 16 and then daily for 7 consecutive days prior to the Week 24, Week 32, Week 40, and Week 48/PD visits.
- c. Analgesic use for HS-related pain is collected daily from at least 7 consecutive days prior to Baseline through Week 16.
- d. HSSA is collected for 7 consecutive days prior to Baseline, Week 2, Week 4, Week 8, Week 12, Week 16, Week 24, and Week 48/PD visits.
- e. For all females of childbearing potential, collect urine for pregnancy test (refer to Section 3.19 for additional details).
- f. If urine pregnancy tests cannot be performed on-site or at home due to COVID-19, urine pregnancy tests may be performed by a local lab.
- g. Samples should be collected pre-dose.

diary

No use or disclosure outside AbbVie is permitted without prior written authorization from AbbVie.

WEEK 8a:

□ INTERVIEW	# AE assessment # Concomitant therapy	# Review and document continued compliance with pregnancy avoidance recommendations in the source records with females of childbearing potential
■ PRO	 PGA Skin Pain^b Analgesic Use^c 	• HSSA ^d
* EXAM	WeightVital signs	 Inflammatory lesion count (abscess, inflammatory nodule, and draining fistula/tunnel count)

0000000000

hsCRP

Blood samples for PK assay^g

5 LOCAL LAB

#,+ Urine pregnancy test^{e,f}

▲ CENTRAL LAB

- + Hematology
- + Blood chemistry
- L Urinalysis
- + Urinalysis
- **R** TREATMENT
- Dispense study drug and dosing diary

NOTES:

- a. Subjects will be brought back to their original visit schedule (calculated from Baseline) if they are out of the visit window, for all visits indicated.
- b. PGA Skin Pain is collected daily from at least 7 consecutive days prior to Baseline through Week 16 and then daily for 7 consecutive days prior to the Week 24, Week 32, Week 40, and Week 48/PD visits.
- c. Analgesic use for HS-related pain is collected daily from at least 7 consecutive days prior to Baseline through Week 16.
- d. HSSA is collected for 7 consecutive days prior to Baseline, Week 2, Week 4, Week 8, Week 12, Week 16, Week 24, and Week 48/PD visits.
- e. For all females of childbearing potential, collect urine for pregnancy test (refer to Section 3.19 for additional details).
- f. If urine pregnancy tests cannot be performed on-site or at home due to COVID-19, urine pregnancy tests may be performed by a local lab.
- g. Blood samples for PK assay that cannot be performed on-site for a specific visit due to COVID-19 will be considered missed.

WEEK 12a:

□ INTERVIEW	AE assessmentConcomitant therapy	 Review and document continued compliance with pregnancy avoidance recommendations in the source records with females of childbearing potential
■ PRO	 PGA Skin Pain^b Analgesic Use^c HSSA^d 	HSIADLQI
* EXAM	WeightVital signsPhysical examination	 Inflammatory lesion count (abscess, inflammatory nodule, and draining fistula/tunnel count) Hurley stage
LOCAL LAB	#,+ Urine pregnancy test ^e	
▲ CENTRAL LAB	 Hematology Blood chemistry Urinalysis HBV testing, where required^f hsCRP Total cholesterol, HDL-C, LDL-C, and triglycerides (fasting) 	 Blood samples for PK assay Optional blood samples for biomarkers:^g whole blood RNA, whole blood DNA, plasma/serum proteomic, IgG and B cell subsets, and PBMC
R TREATMENT	Study drug reassignmentDispense study drug and dosing	

0000000000

NOTES:

All Week 12 procedures must be performed on-site.

diary

- a. Subjects will be brought back to their original visit schedule (calculated from Baseline) if they are out of the visit window, for all visits indicated.
- b. PGA Skin Pain is collected daily from at least 7 consecutive days prior to Baseline through Week 16 and then daily for 7 consecutive days prior to the Week 24, Week 32, Week 40, and Week 48/PD visits.
- c. Analgesic use for HS-related pain is collected daily from at least 7 consecutive days prior to Baseline through Week 16.
- d. HSSA is collected for 7 consecutive days prior to Baseline, Week 2, Week 4, Week 8, Week 12, Week 16, Week 24, and Week 48/PD visits.
- e. For all females of childbearing potential, collect urine for pregnancy test (refer to Section 3.19 for additional details).
- f. Where mandated by local requirements, subjects with HBs Ab+ and/or HBc Ab+ and negative HBV DNA at Screening should have HBV DNA PCR testing performed every 12 weeks. HBV DNA PCR testing every 12 weeks is not necessary when the subject has a history of HBV vaccine and HBs Ab+ and HBc Ab-.
- g. Samples should be collected pre-dose.

WEEK 16a:

□ INTERVIEW	# AE assessment # Concomitant therapy	# Review and document continued compliance with pregnancy avoidance recommendations in the source records with females of childbearing potential
■ PRO	 PGA Skin Pain^b Analgesic Use^c HSSA^d 	# HSIA # DLQI
* EXAM	WeightVital signs	 Inflammatory lesion count (abscess, inflammatory nodule, and draining fistula/tunnel count)
LOCAL LAB	#,+ Urine pregnancy test ^{e,f}	
∠ CENTRAL LAB	 + Hematology^g + Blood chemistry 	 hsCRP Blood samples for PK assay^h

0000000000

NOTES:

R TREATMENT

a. Subjects will be brought back to their original visit schedule (calculated from Baseline) if they are out of the visit window, for all visits indicated.

Dispense study drug and dosing

Urinalysis

diary

- b. PGA Skin Pain is collected daily from at least 7 consecutive days prior to Baseline through Week 16 and then daily for 7 consecutive days prior to the Week 24, Week 32, Week 40, and Week 48/PD visits.
- c. Analgesic use for HS-related pain is collected daily from at least 7 consecutive days prior to Baseline through Week 16.
- d. HSSA data collection for 7 consecutive days prior to Baseline, Week 2, Week 4, Week 8, Week 12, Week 16, Week 24, and Week 48/PD visits.
- e. For all females of childbearing potential, collect urine for pregnancy test (refer to Section 3.19 for additional details).
- f. If urine pregnancy tests cannot be performed on-site or at home due to COVID-19, urine pregnancy tests may be performed by a local lab.
- g. Additional clinical hematology tests are recommended at Week 20 (unscheduled visit) for subjects who have absolute neutrophil counts < 1,200 μ L or hemoglobin < 9 g/dL at Week 16.
- h. Blood samples for PK assay that cannot be performed on-site for a specific visit due to COVID-19 will be considered missed.

۱۸	/F	Fk	()	∕la.

00	00	\sim	\bigcirc	\cap	\bigcirc	\circ	\cap
\circ	$O_{\mathcal{C}}$		\cup	\mathcal{O}	\cup	\cup	\cup

□ INTERVIEW	# AE assessment # Concomitant therapy	# Review and document continued compliance with pregnancy avoidance recommendations in the source records with females of childbearing potential
■ PRO	PGA Skin Pain ^b	• HSSA ^c
* EXAM	WeightVital signs	 Inflammatory lesion count (abscess, inflammatory nodule, and draining fistula/tunnel count)
LOCAL LAB	#,+ Urine pregnancy test ^{d,e}	
▲ CENTRAL LAB	 Hematology Blood chemistry Urinalysis HBV testing, where required^f hsCRP Total cholesterol, HDL-C, LDL-C, and triglycerides (fasting) 	 Blood samples for PK assay^g Optional blood samples for biomarkers:^h whole blood RNA, whole blood DNA, plasma/serum proteomic, IgG and B cell subsets, and PBMC
R TREATMENT	Dispense study drug and dosing	

NOTES:

- a. Subjects will be brought back to their original visit schedule (calculated from Baseline) if they are out of the visit window, for all visits indicated.
- b. PGA Skin Pain is collected daily from at least 7 consecutive days prior to Baseline through Week 16 and then daily for 7 consecutive days prior to the Week 24, Week 32, Week 40, and Week 48/PD visits.
- c. HSSA data collection for 7 consecutive days prior to Baseline, Week 2, Week 4, Week 8, Week 12, Week 16, Week 24, and Week 48/PD visits.
- d. For all females of childbearing potential, collect urine for pregnancy test (refer to Section 3.19 for additional details).
- e. If urine pregnancy tests cannot be performed on-site or at home due to COVID-19, urine pregnancy tests may be performed by a local lab.
- f. Where mandated by local requirements, subjects with HBs Ab+ and/or HBc Ab+ and negative HBV DNA at Screening should have HBV DNA PCR testing performed every 12 weeks. HBV DNA PCR testing every 12 weeks is not necessary when the subject has a history of HBV vaccine and HBs Ab+ and HBc Ab-.
- g. Blood samples for PK assay that cannot be performed on-site for a specific visit due to COVID-19 will be considered missed.
- h. Samples should be collected pre-dose.

diarv

WEEK 32a:

00	00	\mathcal{L}	00	\sim		\cap
\circ	\mathcal{O}		\mathcal{O}		\cup	\cup

□ INTERVIEW	# AE assessment # Concomitant therapy	# Review and document continued compliance with pregnancy avoidance recommendations in the source records with females of childbearing potential
■ PRO	PGA Skin Pain ^b	
** EXAM	WeightVital signs	 Inflammatory lesion count (abscess, inflammatory nodule, and draining fistula/tunnel count) Hurley Stage
5 LOCAL LAB	#,+ Urine pregnancy test ^{c,d}	
▲ CENTRAL LAB	+ Hematology+ Blood chemistry+ Urinalysis	• hsCRP
R TREATMENT	Dispense study drug and dosing	

NOTES:

a. Subjects will be brought back to their original visit schedule (calculated from Baseline) if they are out of the visit window, for all visits indicated.

diary

- b. PGA Skin Pain is collected daily from at least 7 consecutive days prior to Baseline through Week 16 and then daily for 7 consecutive days prior to the Week 24, Week 32, Week 40, and Week 48/PD visits.
- c. For all females of childbearing potential, collect urine for pregnancy test (refer to Section 3.19 for additional details).
- d. If urine pregnancy tests cannot be performed on-site or at home due to COVID-19, urine pregnancy tests may be performed by a local lab.

WEEK 40a:

Ω			\wedge			\wedge		\cap
00	\cup	\cup	\cup	\cup	\cup	\cup	\cup	\cup

□ INTERVIEW	# AE assessment # Concomitant therapy	# Review and document continued compliance with pregnancy avoidance recommendations in the source records with females of childbearing potential
■ PRO	PGA Skin Pain ^b	
* EXAM	WeightVital signs	 Inflammatory lesion count (abscess, inflammatory nodule, and draining fistula/tunnel count)
5 LOCAL LAB	#,+ Urine pregnancy test ^{c,d}	
▲ CENTRAL LAB	+ Hematology+ Blood chemistry+ Urinalysis	• hsCRP
R TREATMENT	 Dispense study drug and dosing diary 	

NOTES:

- a. Subjects will be brought back to their original visit schedule (calculated from Baseline) if they are out of the visit window, for all visits indicated.
- b. PGA Skin Pain is collected daily from at least 7 consecutive days prior to Baseline through Week 16 and then daily for 7 consecutive days prior to the Week 24, Week 32, Week 40, and Week 48/PD visits.
- c. For all females of childbearing potential, collect urine for pregnancy test (refer to Section 3.19 for additional details).
- d. If urine pregnancy tests cannot be performed on-site or at home due to COVID-19, urine pregnancy tests may be performed by a local lab.

WEEK 48^a/PREMATURE DISCONTINUATION:

INTERVIEW	# AE assessment # Concomitant therapy	# Review and document continued compliance with pregnancy avoidance recommendations in the source records with females of childbearing potential
■ PRO	 PGA Skin Pain^b HSSA^c 	Collect ePRO device
* EXAM	WeightVital signsPhysical examination	
5 LOCAL LAB	#,+ Urine pregnancy test ^{d,e}	
▲ CENTRAL LAB	 Hematology Blood chemistry Urinalysis HBV testing, where required^f hsCRP Total cholesterol, HDL-C, LDL-C, and triglycerides (fasting) 	Optional blood samples for biomarkers: whole blood RNA, plasma/serum proteomic, and IgG and B cell subsets

NOTES:

- a. Subjects will be brought back to their original visit schedule (calculated from Baseline) if they are out of the visit window, for all visits indicated.
- b. PGA Skin Pain is collected daily from at least 7 consecutive days prior to Baseline through Week 16 and then daily for 7 consecutive days prior to the Week 24, Week 32, Week 40, and Week 48/PD visits.
- c. HSSA data collection for 7 consecutive days prior to Baseline, Week 2, Week 4, Week 8, Week 12, Week 16, Week 24, and Week 48/PD visits.
- d. For all females of childbearing potential, collect urine for pregnancy test (refer to Section 3.19 for additional details).
- e. If urine pregnancy tests cannot be performed on-site or at home due to COVID-19, urine pregnancy tests may be performed by a local lab.
- f. Where mandated by local requirements, subjects with HBs Ab+ and/or HBc Ab+ and negative HBV DNA at Screening should have HBV DNA PCR testing performed every 12 weeks. HBV DNA PCR testing every 12 weeks is not necessary when the subject has a history of HBV vaccine and HBs Ab+ and HBc Ab-.

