5.6 Follow-Up After Subject Discontinuation of Study Drug or from Study

Discontinuation of Study Drug and Continuation of Study Participation

To minimize missing data for efficacy and safety assessments, subjects who prematurely discontinue study drug treatment should continue to be followed for all regularly scheduled visits as outlined in the Activity Schedule (Appendix D), unless subjects have decided to discontinue study participation entirely (withdrawal of informed consent). Subjects should be advised on the continued scientific importance of their data even if they discontinue treatment with study drug early. Following discontinuation of study drug, the subject should be treated in accordance with the investigator's best clinical judgment irrespective of whether the subject decides to continue participation in the study.

Premature Discontinuation of Study (Withdrawal of Informed Consent)

If a subject prematurely discontinues study participation (withdrawal of informed consent), the procedures outlined for the Premature Discontinuation visit should be completed as soon as possible, preferably within 2 weeks. In addition, if subject is willing, a 30-day follow-up visit (or phone call if a visit is not possible) after the last dose of study drug may be completed to determine the status of any ongoing AEs/serious adverse events (SAEs) or the occurrence of any new AEs/SAEs.

For subjects to be considered lost to follow-up, reasonable attempts must be made to obtain information on the subject's final status. At a minimum, 2 telephone calls must be made and 1 certified letter must be sent and documented in the subject's source documentation.

In the event a subject withdraws consent from the clinical study, biomarker research will continue unless the subject explicitly requests analysis to be stopped. When AbbVie is informed that samples are withdrawn from research, samples will not be analyzed, no new biomarker analysis data will be collected, and the samples will be destroyed. A subject may withdraw consent for optional biomarker research at any time and remain in the clinical study. Data generated from clinical study and/or optional biomarker research, before subject withdrawal of consent, will remain part of the study results.

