APPENDIX D. ACTIVITY SCHEDULE

The following table shows the required activities across all visits. The individual activities are described in detail in the Operations Manual (Appendix F). Allowed modifications due to COVID-19 are detailed within the Operations Manual.

Study Activities Table

Activity	Day –35 to Screening	Day 1 Baseline	Day 15 Week 2 ^a	Day 29 Week 4 ^a	Day 57 Week 8 ^a	Day 85 Week 12 ^a	Day 112 Week 16 ^a	Day 168 Week 24 ^a	Day 224 Week 32 ^a	Day 280 Week 40 ^a	Week 48 ^a / Day 336 Premature Discontinuation	30-Day Follow Up Visit/Call
Visit Window	۵ ۵	Ď		Days	Ď	Ď	Ds	Ď	±7 Day		Ds	30 Vis
				Jays					± / Da\	13		
□ INTERVIEWS & (QUEST	IONNA	IRES									
Informed consent	✓											
Eligibility criteria	✓	✓										
Medical/surgical history	✓	\										
Hidradenitis suppurativa history	✓	>										
Alcohol and nicotine use	✓											
Adverse event assessment	*	*	*	*	*	*	*	*	*	1	*	*
Prior/concomitant therapy	1	1	1	1	1	*	1	*	1	*	*	1
Analgesic use (for HS-related pain) – daily from at least 7 consecutive days prior to Baseline and up to Week 16	*	*	*	*	*	*	*					
Patient Reported Outcomes (PROs): PGA Skin Pain— daily from at least 7 consecutive days prior to Baseline and up to Week 16; afterwards for 7 consecutive days leading up to each visit	*	1	*	*	*	*	*	*	1	*	*	

											ion	
Activity	Screening	Baseline	Week 2 ^a	Week 4 ^a	Week 8 ^a	Week 12 ^a	Week 16 ^a	Week 24 ^a	Week 32 ^a	Week 40ª	Week 48 ^a / Premature Discontinuation	w Up
	Day -35 to Day -1	Day 1	Day 15	Day 29	Day 57	Day 85	Day 112	Day 168	Day 224	Day 280	Day 336	30-Day Follow Up Visit/Call
PROs: HSSA – 7 consecutive days prior to Baseline, Week 2, Week 4, Week 8, Week 12, Week 16, Week 24, and Week 48/PD visits	~	V	V	*	*	*	V	*			*	
PROs: HSIA		✓		✓		✓	✓					
PROs: DLQI		✓				✓	✓					
Dispense handheld ePRO device and the paper diary (for Analgesic Use for HS-related pain)	*											
Collect handheld ePRO device											*	
TB risk assessment questionnaire	✓											
Review and document pregnancy avoidance recommendations with females of childbearing potential	*	*	1	*	*	*	V	*	*	*	*	
TLOCAL LABS &	EXAM	S										
Chest x-ray	✓											
12-lead ECG	✓											
Height (screening only) and weight	*	*	✓	*	*	*	*	*	*	*	✓	
Vital signs	✓	✓	✓	✓	✓	✓	✓	*	*	>	✓	
Physical examination	✓	✓				✓					✓	
Investigator assessments (abscess, inflammatory nodule, and draining fistula/tunnel count)		✓	✓	✓	1	1	√	✓	1	√		
Hurley Stage		✓				1			1			

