3.17 Handheld ePRO Device

During the Screening Visit, subjects will be dispensed a handheld ePRO device to collect information about PGA Skin Pain and HSSA. PGA Skin Pain information will be collected daily from at least 7 consecutive days before the Baseline visit through the Week 16 visit. Post-Week 16 visit, PGA Skin Pain will be collected for 7 consecutive days prior to the scheduled visits outlined in Section 2.1. HSSA will be collected daily for 7 consecutive days prior to the scheduled visits outlined in Section 2.1. At

No use or disclosure outside AbbVie is permitted without prior written authorization from AbbVie.

each visit, site representatives should check to see that subjects have performed the required assessments between study visits.

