3.20 Subject Withdrawal from Study

All attempts must be made to determine the date of the last study drug dose and the primary reason for discontinuation of study drug or study participation. The information will be recorded on the appropriate eCRF page. However, these procedures should not interfere with the initiation of any new treatments or therapeutic modalities that the investigator feels are necessary to treat the subject's condition. Following discontinuation of study drug, the subject should be treated in accordance with the investigator's best clinical judgment irrespective of whether the subject decides to continue participation in the study.

Premature Discontinuation of Study (Withdrawal of Informed Consent)

Subjects may withdraw from the study completely (discontinuation of study drug treatment and study participation; withdrawal of informed consent) for any reason at any time. If a subject prematurely discontinues study participation, the procedures outlined for the Premature Discontinuation visit (PD visit) should be completed as soon as possible, preferably within 2 weeks of study drug discontinuation. In addition, a 30-day follow-up visit (or phone call if a visit is not possible) should occur to determine the status of any ongoing AEs/SAEs or the occurrence of any new AEs/SAEs. Subjects who discontinue the study prematurely after randomization will not be replaced.

Discontinuation of Study Drug and Continuation of Study Participation

Subjects may discontinue study drug treatment but may choose to continue to participate in the study.

Subjects who prematurely discontinue study drug should complete a Premature Discontinuation visit (PD visit) as soon as possible, preferably within 2 weeks. Afterwards, subjects should follow the regular visit schedule as outlined in the Protocol Study Activities Table and adhere to all study procedures except for dispensing study drug, PK sample collection, and blood sample collection for optional exploratory research and validation studies. Female subjects who discontinue study drug due to pregnancy will not undergo additional imaging tests. Once the subject has discontinued study drug, subjects should be treated per standard of care. If at any point a subject no longer wants to provide assessments (withdrawal of informed consent) following discontinuation of study drug, a second PD visit is not required.

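### The visit list collects the handheld ePRO device at the Premature Discontinuation visit, but subjects who stop drug and stay in the study must still record skin pain and HSSA on it; the two instructions conflict

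*Protocol*

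**What the plan says.** **Device collection.** The Operations Manual 2.1 list for the combined Week 48/PD visit includes "Collect ePRO device". The Protocol Appendix D row "Collect handheld ePRO device" is ticked only in the Week 48/PD column. Neither has a footnote for subjects who continue in the study.

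**Who attends a PD visit.** Operations Manual 3.20, in its paragraph on stopping drug while continuing participation, says: "Subjects who prematurely discontinue study drug should complete a Premature Discontinuation visit (PD visit) as soon as possible, preferably within 2 weeks". Those subjects then return to the regular schedule and "adhere to all study procedures except for dispensing study drug, PK sample collection, and blood sample collection for optional exploratory research". Patient-reported outcomes are not among the exemptions.

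**Why follow-up continues.** Protocol 5.6: "To minimize missing data for efficacy and safety assessments, subjects who prematurely discontinue study drug treatment should continue to be followed" at all scheduled visits.

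**What the device does.** Under Operations Manual 3.17, at Screening "subjects will be dispensed a handheld ePRO device to collect information about PGA Skin Pain and HSSA". Skin pain is due daily through Week 16, so the Week 12 window is covered. Appendix D shows the device being dispensed at Screening only.

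**How a gap is scored.** NRI-C is the primary missing-data method for NRS30 (SAP 9.4.1). Under SAP 9.2.1 a subject with no evaluation in the visit window is a non-responder, with two exceptions: a responder both before and after the window, and data missing because of COVID-19, which are multiply imputed.

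**The concern.** A logistics line in a visit checklist can remove data that the rest of the protocol asks for. Only two events make a subject a non-responder at later visits under SAP 9.2.1: starting antibiotics for HS-related infection, and stopping drug for lack of efficacy. Stopping drug for another reason, such as an adverse event, is not on that list, so an observed Week 12 pain score from such a subject should count. If the device has been handed in, that score cannot be entered by any route the documents describe, and the subject becomes a failure by default.

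NRS30 is the only secondary endpoint. Lesion counts are made by the investigator and continue, so the same subject could be assessed on observed data for HiSCR and on imputation for NRS30. HSSA feeds four of the additional endpoints (total, swelling, odor, worst drainage), and for these subjects it would end at the PD visit.

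**Working it through.** **1. Is there another way to record the data?** The paper diary is for analgesic use. The phone or video option in Operations Manual 3.7 names DLQI and HSIA only, and not at Baseline or Week 12. No section re-issues a device or lets a continuing subject keep it. So no alternative is stated for PGA Skin Pain or HSSA.

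**2. Do the SAP rules recover the loss?**
- The before-and-after exception needs a later response. None can be recorded, and SAP Appendix E 2.1 confines the exception to the same study period.
- The full multiple-imputation sensitivity analysis is for the primary endpoint only (SAP 9.2.1, 9.3.3). For NRS30 the sensitivity analysis is NRI-NC, which also scores the gap as failure.
- HSSA is analysed by MMRM on observed values. Values before the PD visit stay in; later ones are missing.

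**3. Who is affected?** Only subjects meeting all of these conditions:
- baseline NRS of at least 3;
- drug stopped for a reason other than lack of efficacy (already a non-response) or COVID-19 (imputed);
- still in the study (a subject who withdraws consent has no Week 12 score either way);
- device handed in before enough Week 12 diary days exist;
- not already a non-responder at Week 12 under the antibiotic or analgesic rules.

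**4. Size.** The documents give no figure for this point. As a check on method, I first reproduce the stated HiSCR power (Protocol 7.7: n = 40, 57% against 25%, one-sided 0.05):

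power = Φ{[(p1 − p0)√n − 1.645√(p0(1 − p0))] / √(p1(1 − p1))} = 99.6%, consistent with the stated figure of more than 95%.

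Inputs for NRS30: null rate 22.5% (SAP 9.4.1); upadacitinib rate 46% (SAP Appendix F 3.2). Assumptions: n = 40 with baseline NRS of at least 3 (an upper figure for the planned arm), m = 2 to 4 affected, and an off-drug response rate q between 22.5% and 46%.

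Responders lost = m × q; points lost = 100 × m × q / 40.

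| m | q | Responders lost | Points lost |
|---|---|---|---|
| 2 | 22.5% | 0.45 | 1.1 |
| 2 | 46% | 0.92 | 2.3 |
| 4 | 22.5% | 0.90 | 2.3 |
| 4 | 46% | 1.84 | 4.6 |

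The critical count comes from z = (x/40 − 0.225)/√(0.225 × 0.775/40), where the denominator is 0.0660. At x = 14, z = 1.89 and p = 0.029; at x = 13, z = 1.51 and p = 0.065. So 14 or more is significant. The exact binomial chance of reaching 14 is:

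| m | Device collected (m forced failures) | Device kept, q = 22.5% | Device kept, q = 46% |
|---|---|---|---|
| 0 | 94.1% | n/a | n/a |
| 2 | 90.3% | 92.3% | 94.1% |
| 4 | 84.7% | 90.0% | 94.1% |

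The avoidable loss of power is therefore 92.3 − 90.3 = 2.0 to 94.1 − 90.3 = 3.8 points for m = 2, and 90.0 − 84.7 = 5.3 to 94.1 − 84.7 = 9.4 points for m = 4. With the 45 upadacitinib subjects used in the SAP simulations and 10% affected, the normal approximation gives 88.1% with the device collected, against 93.0% to 96.3% with it kept.

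**The case against.** The best reply is that the text is ambiguous and does not make the data impossible. Operations Manual 3.20 keeps patient-reported outcomes in force after the PD visit, and 3.17 asks sites to check at each visit that the assessments were done, so a sensible site may leave the device with a continuing subject. Protocol 5.6 mentions PD-visit procedures only for withdrawal of consent, where collecting the device is right. The clash arises because 3.20 uses the same combined visit for drug-only stops. That stands: the finding is a conflict between instructions, and the loss occurs only where a site follows the visit list. Nothing tells the site which instruction prevails.

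Three stronger readings are tempting, and the documents do not support them:
- *Every stop before Week 12 becomes an NRS30 failure.* Step 3 of the working shows that only a subset is affected. SAP Appendix E 2.1 expressly includes COVID-19-related drug discontinuations among the gaps to be imputed.
- *These subjects drop out of the HSSA analysis.* Only values after the PD visit are lost.
- *One subject decides the result.* The step from 14/40 to 13/40 is the critical boundary, where one subject always decides. At 46% about 18 of 40 respond; 16/40 and 17/40 still give p = 0.004 and 0.001.

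The paper analgesic diary is not part of the problem, because no section collects it at the PD visit.

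**Conclusion.** The conflict is real and worth correcting. Appendix D and Operations Manual 2.1 take the device at a visit that 3.20 also assigns to subjects whose skin pain and HSSA are still required, and no substitute is given. If the visit list is followed, the subset in step 3 become NRS30 non-responders by a rule the SAP did not choose.

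On the stated assumptions the cost is about 0.5 to 2 upadacitinib responders, or 1 to 5 percentage points. The count of 2 to 4 in 40 and the off-drug response rate are assumptions; the documents supply neither. Against the fixed 22.5% rate the effect can only lower the upadacitinib rate. In the in-trial and pooled comparisons its direction depends on discontinuation by arm. A lower in-trial placebo rate could also raise the number of synthetic placebo subjects allowed under the 36% and 37% cut-offs in SAP 9.4.1. HiSCR, and so the primary analysis, is untouched.

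**What to change.** In Protocol Appendix D and the Operations Manual 2.1 Week 48/PD list, add a footnote: collect the device at Week 48, or at the PD visit only if the subject is leaving the study. In Operations Manual 3.20, add one sentence: subjects who stop study drug but continue participation keep the handheld device and go on recording PGA Skin Pain and HSSA on schedule.

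The cost is one footnote and one sentence, with some devices out longer. It adds no procedure or subject burden beyond what 3.20 already requires, and the SAP needs no change.
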